The PI/Co-PI and project staff will remain blinded and only the study statistician will have access to unblinded data. Should statistically significant differences arise during the interim analyses, these results will be shared with the IRBs at CDN and the health centers, and a decision to terminate the study will be made at that time. The DSMP developed will be designed to ensure the health and safety of research participants, and it will be designed collaboratively, with involvement of all investigators and the Stakeholder Working Group.

J. POTENTIAL CONFLICT OF INTEREST

None noted.

K. LOCATION OF THE STUDY

The primary institution of the PI, CDN, has seven contractual agreements that bring together community organizations, mental health experts, community health centers, and an academic university with faculty expertise in cross-sector partnerships and biostatistics. The PI, [name], along with his parent institution, CDN, as well as the contractors and their parent institutions are all aware of and agree on the appropriate programmatic and administrative personnel at each organization involved in the PCORI application and are aware of the applicant organization's consortium agreement policy. Should this study be funded, all agencies and individuals are prepared to establish the necessary inter-organizational agreement consistent with that policy.

Practice Sites

The proposed study brings together six practices, including two federally qualified health centers (Urban Health Plan, Inc. and Morris Heights Health Center), two Diagnostic and Treatment Centers that have FQHC look-alike designation (Segundo Ruiz Belvis and Morrisania D&TCs) and two ambulatory care practices (Montefiore Family Care Center and Lincoln Ambulatory Practice) to be the recruitment

sites for this study. These centers bring their years of expertise delivering primary and specialty care to the residents of the Bronx and will act as the medical providers for all participants in this study. Briefly, **Urban Health Plan, (UHP)**, is a network of community health centers in the Bronx and Queens, NY (this study will work with all of UHP's Bronx based sites). The mission of UHP is to improve the health status of underserved communities. As a Federally Qualified Health Center (FQHC) and a level III patient centered medical home, UHP offers a broad array of primary and preventative medical services, dental, mental health and specialty services. In 2011, UHP served 48,000 patients through 250,000 patient visits at eight clinic sites, seven school-based clinics, and four off-sites (e.g., homeless shelters, adult day care centers). UHP was one of the first FQHCs in the country to implement an EHR.

As a result, UHP is in a unique position to assist in customizing systems to meet the service-reporting and quality improvement demands of both New York State and the Federal government. In fact, UHP is nationally recognized for its quality improvement initiatives (QI) and has conducted QI initiatives for both cancer screening and mental health. This expertise and experience with QI is a great strength that UHP will bring to this study as both a recruitment and intervention site and as a key stakeholder. Like UHP, **Morris Heights Health Center (MHHC)** is also a non-profit organization, a Federally Qualified Health Center, and a level III patient centered medical home. It has been a leading provider of primary healthcare to Morris Heights and the surrounding areas in the Bronx since 1981, and its mission is to provide high-quality, affordable, and accessible healthcare to all. The Center serves more than 48,000 patients annually, 76% of whom live at, or under, the poverty level providing primary, specialty, dental, mental health, educational and social services. MHHC is unique in the Bronx in that it operates both article 28 and article 31 mental health clinics. As a result, they bring not only expertise providing care to their patients and the community, but also an in depth understanding of the mental health care system in the Bronx. As the largest and oldest ambulatory care teaching site in the Montefiore system, the Montefiore **Family Care Center (FCC)** brings the unique strength and perspective of an academic teaching center. Like UHP and MHHC, FCC serves a primarily low-income population providing both primary and specialty care services. In 2011 the Adult Medical Practice had nearly 45,000 visits serving approximately 15,000 unique patients. CDN, the lead institution, has long-standing collaborative relationships with UHP, MHHC, and Montefiore.

Lincoln Hospital Ambulatory Care Services, Morrisania Diagnostic and Treatment Center and Segundo Ruiz Belvis Diagnostic and Treatment Center are part of NYC Health + Hospitals Corporation and have a longstanding history of providing quality comprehensive medical care to low income and underserved patients in the Bronx.

L. POTENTIAL RISKS

There are no physical risks posed by this study, and the risks of participation are minimal. However, we are targeting patients with depression who may report experiencing distress during an in-person or phone interview with study staff, or during a phone or in-person visit with a care manager. The level of distress participants may experience can range from minimal distress (fleeting and not disruptive to the patient's functioning) to significant distress (patient is unable to refocus and activities are disrupted). Our experience from prior research studies is that such extreme reactions are very rare; however, patients who experience distress at any of the study visits will be referred to their Primary Care Clinician for follow-up care. An Emergency Protocol has been developed detailing the steps and key personnel that need to be contacted in the event of an emergency, such as suicidal thoughts.

M. POTENTIAL BENEFITS

Although we cannot guarantee benefits from participation in this study, all participants will be randomized to one of the intervention conditions and will receive care management services with a focus on cancer screening, or on cancer screening and depression management. All participants will receive information about cancer screening and support to help them make cancer screening decisions. Some participants will also receive information about depression and depression care management.

N. ALTERNATIVE THERAPIES

N/A

O. COMPENSATION TO SUBJECTS

All women screened will receive \$5 for their time. Patients will receive \$10 for participating in the first and second interviews and \$15 for the third interview.

P. COSTS TO SUBJECTS

The cost to each patient for taking part in this project is the time spent with the Care Manager, the time spent taking the screening tests, and the time spent answering the questions during the three (3) interviews. If the patient has health insurance, the screening tests will be covered by the patient's insurance. If the patient does not have health insurance, we will work with the patients and their practices to find ways to pay for the breast, cervical, and colon cancer screening tests they need.

Q. RADIATION OR RADIOACTIVE SUBSTANCES

N/A

REFERENCES

1. U.S. Census 2010: State and County QuickFacts, Bronx, NY. U.S. Census Bureau, 2010. (Accessed at <http://quickfacts.census.gov/qfd/states/36/36005.html>.)
2. Macri Jea. Health Insurance Coverage in New York, 2009; 2011.

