C. STUDY PROCEDURES

Female patients ages 50-64 years of age and identified as out-of-adherence with at least one cancer screening based on the CHCs' electronic medical records will be recruited by care managers in the waiting room or by telephone following a mailed letter. Care managers will receive verbal consent to administer a brief screening tool to assess eligibility for the study, as outlined above; these data will be anonymized, so that it will not be possible to link the screening data back to the individual patient. All women screened will receive \$5 for their time. Patients who are not eligible for the study but whose score on the PHQ-9 is indicative of depression (≥ 8) will be asked if they would like help making an appointment at the CHC.

All women who agree to participate in this study will complete a process of informed consent, during which the care manager will discuss the study and its potential risks and benefits, and answer any questions that potential participants might have. It will be made clear that each woman's decision regarding participation in the study will in no way impact her individual access to free or low cost medical care at that particular health center where consent is taking place, or at any other health center. The consent form, like the survey instruments, will be available to participants in English or in Spanish.

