F. STUDY QUESTIONNAIRES AND MEASUREMENT

We chose measures that are based on the conceptual model, have been validated and used widely with minority populations, and have been translated into Spanish; as needed, we will use a translating service with forward and back translation to translate the measures. All items taken from the National Cancer Institute's HINTS survey have been translated. We organize the measures by: primary outcomes, intermediate outcomes, and co-variables.

Primary Outcomes

Participation in colorectal, breast, and cervical cancer screening

We will assess participation in age-appropriate cancer screening behaviors in two ways:

a. Chart Review: Review of electronic medical records at each of the three CHCs.

b. Self-Report: We will ask participants about their participation (yes/no) in specific screening methods: Pap testing (past 3 years), mammography (past 2 years), and colorectal screening (FOBT/FIT, past year; flexible sigmoidoscopy, the past 5 years; and colonoscopy, past 10 years). We will use standardized items from the NCI's HINTS Survey.¹²⁷

Depression

a. Patient Health Questionnaire (PHQ)-9. The PHQ-9 is the 9-item depression module from the full PHQ, and is a well-validated Diagnostic and Statistical Manual of Mental Disorders 4th Edition (DSM-IV) criterion-based measure for screening and diagnosing depressive episode, assessing severity, and monitoring treatment response,^{128,129,130,131} either in person or over the phone.¹³² It has been shown to measure a common concept of depression across racial and ethnic groups, including African Americans and Latinos.^{128,133} Cronbach's alpha was 0.80 in both African American and Latino samples.¹²⁸ As a severity measure, the score can range from 0-27, since each of the 9 items can be scored from 0 (not at all) to 3 (nearly every day). Meta-analysis showed pooled sensitivity of 0.80 and specificity of 0.92 to a diagnosis of major depression among primary care patients in a structured psychiatric interview by a mental health professional using DSM-IV diagnostic criteria.¹³¹ As a practical screening tool, patients with a score of > 10 are considered to have clinically significant depressive symptoms.^{99,134,96,112,135,129}

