b. The Hopkins Symptom Checklist (SCL-20). The SCL-20 consists of the 20 depression items on a 4-point scale from the SCL-90, and has been shown to be a valid and reliable measure of depression in diverse outpatient and community populations (Cronbach's alpha = 0.87; test-retest r=0.81).^{136,137} It has been shown to be sensitive to change in studies of collaborative care in primary care settings^{99,97,121,96,112,134,135} and among minority group patients.^{95,99,133}

We will consider clinically meaningful improvement of depressive symptoms to be a > 50% reduction in baseline SCL-20 or PHQ-9, and depression remission as an SCL-20 score <0.5 or a PHQ-9<5.

Intermediate Outcomes

Quality of Life/Health Status. We will measure quality of life with the Medical Outcomes Study (MOS) Short Form Health Survey (SF-12), which includes heterogeneous items from the SF-36 physical and mental component scales. This general measure of health status assesses the patient's perceived health status and whether health problems interfere with normal functioning. The SF-12 has with demonstrated validity and test-retest reliability in the general population and in patients with chronic health conditions, and has been tested in five languages, including Spanish.¹³⁸ It has been used extensively as a quality of life measure in collaborative care studies,⁴² including with low-income minority populations.^{95,99} It has also been used frequently in screening studies, for cancer and other conditions.¹³⁹⁻¹⁴² The SF-12 has been validated as an indicator of effects of depression on quality of life in ethnically diverse patients.¹⁴³

Mental Health Care Utilization.

We will assess mental health care utilization in two ways:

c. Chart review. We will use data from the electronic medical record to determine the number of health visits, and the kind of provider seen for mental health care (psychiatrist, psychologist, and/or clinical social worker).

d. Patient report. At baseline, we will ask respondents how many times in the past six months they have seen a provider to talk about or get medication for feeling sad, nervous, hopeless, or blue. In addition, we will ask participants about their ability to arrange to get mental health treatment, as well as whether they

have the financial resources to access mental health services. These questions will be adapted from the NCI's HINTS survey.¹²⁷

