We will recruit 800 women to the study. To be eligible for the study, women must be patients at one of the six participating Bronx CHCs. They must also be between 50 and 64 years of age, speak English or Spanish, reside in the Bronx, screen positive for depression based on the PHQ-9 (≥ 8) at time of recruitment, and be out-of-adherence with current U.S. Preventive Services Task Force cancer screening guidelines for breast, cervical, and/or colorectal cancer screening. Women will be considered out of adherence if they have not received a Pap test without HPV in the past three years or a Pap test with HPV in the past five years, a mammogram in the past two years, and/or one of the following forms of colorectal screening: FOBT (or FIT) within the past year, flexible sigmoidoscopy in the past five years, or colonoscopy in the past 10 years. A woman who has had total hysterectomy is considered up-to-date for cervical cancer screening after the date on which the hysterectomy was performed.⁷⁶ We aim to be as inclusive as possible in this study. However, to maximize feasibility and in keeping with prior collaborative care research^{99,112}, we will exclude women who report the following when screened: terminal illness, current pregnancy (albeit unlikely in this age range), substance use, decisionally impaired or suicidal thoughts. We will exclude prisoners. Data received from the six health center sites support the availability of potential study participants and demonstrate the need for a study such as this one. In 2011, across the study sites, mammography rates for women 50-64 years of age were 56%, 57% and 64%; Pap testing rates were 62%, 50% and 53%. All of these rates fell substantially below the New York City target of 85% or greater. For colon cancer screening, rates in 2011 were 24%, 52%, and 27%, also much lower than the New York City target of 60% or greater. Additionally, depression rates for women of this age range in 2011 were 35% (including dysthymia), 21%, and 21%, which is consistent with the literature.

H. RECRUITMENT OF SUBJECTS

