Participating sites are Morris Heights Health Center, Urban Health Plan and Montefiore Primary Care Practice. We have added Segundo Ruiz Belvis and Morrisania Diagnostic and Treatment Centers and Lincoln Primary Care Practice as three additional sites. We will recruit approximately 800 women ages 50-64 who screen positive for depression and who are non-adherent with cervical, breast, and/or colorectal cancer screening guidelines from one of the participating Bronx sites. Women in this age range should receive all three types of cancer screening. We are focusing solely on women because estimates of depression among minority women in the Bronx are 20%-25%, at least twice that of men, and depression has been shown to be a barrier to screening, with consequences for cancer morbidity and mortality. Patients will be approached and screened in the participating sites in person or by phone to

determine whether they meet initial study inclusion criteria; they will have been identified as potentially eligible by the electronic medical record. Only patients who speak English or Spanish are eligible. For this screening, patients will provide verbal consent; the data will be anonymized. Patients will receive \$5 for their participation in the screening. If a patient confirms through this initial screening that she is out-of-adherence for one or more types of cancer screening (breast, cervical, and/or colorectal), the patient will be administered the Patient Health Questionnaire (PHQ)-9 to determine whether she meets criteria for depression. Those patients who score greater than or equal to 8 on the PHQ-9, do not have a terminal illness, are not pregnant, are not prisoners, are not decisionally impaired and are not active substance users will be asked to provide written informed consent to participate in the study. Patients will be told that study involvement entails speaking with a care manager at least once per month by phone or in-person, as they prefer, and they will be told about the two arms of the study and the randomization process. They will also be informed that participation will involve completing a baseline interview at the time of screening or within the week, as well as two follow-up interviews at 6 and 12-months after the baseline assessment.

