To determine whether reducing depression increases the likelihood that low-income women will receive age-appropriate cancer screening (Aim 3), we included improvement in depression (as well as depression remission in a separate model) in the logistic regression models to examine its association with cancer screenings, and also to examine if the difference between the two intervention arms was modified by change in depression; we examined the interaction between improvement in depression and treatment (as well as depression remission and treatment). To determine whether the effectiveness of the CCI intervention varies according to patient characteristics, such as language spoken and, obesity, etc. (Aim 4), we examined each of these variables as possible effect modifiers. However, it is understood that the statistical power for testing an interaction term may be limited in this study; consequently, this aim was treated as exploratory and the results of this study will be used to design a future, more definitive study with interventions identified and targeted to address issues associated with specific subgroups who may experience reduced benefit from the intervention.

Missing Data

Missing data are a common problem in longitudinal studies. In the context of the present study, missing data will occur when, for example, not all the screening outcomes are reported for a given participant, or some of the co-variables (e.g., body mass index) are missing. For the initial approach in the primary analysis of the study, study participants with missing values on either the outcomes or the co-variables were first removed from the study for the evaluation of intervention effects. However, this approach required the assumption of missing completely at random to be true. A violation of this assumption may lead to bias in the estimate of the intervention effect. We first examined the level of missing data by each outcome and each co-variate in the model. If the rate of missing data is small (<5%), the chance that it will bias the result is very low; however, if the rate of missing data is moderate (>10%), sensitivity analysis was used to examine the robustness of the result. For example, if one variable has a moderate level of missing, we conducted a sensitivity analysis which compared those participants with the remaining participants and also included those participants in the analyses by adding a separate missing category.

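### Remission is defined by an end score alone, so women who already meet it at the baseline interview can count as remitted in the Aim 3 remission model

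*Protocol*

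**What the plan says.** Protocol section F (Primary Outcomes, Depression) gives two definitions. Improvement is tied to baseline: "We will consider clinically meaningful improvement of depressive symptoms to be a > 50% reduction in baseline SCL-20 or PHQ-9". Remission is an end state only: "depression remission as an SCL-20 score <0.5 or a PHQ-9<5". The remission rule sets no starting level and names no visit.

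On entry, section G requires that women "screen positive for depression based on the PHQ-9 (≥ 8) at time of recruitment". Section H repeats the threshold ("Those patients who score greater than or equal to 8 on the PHQ-9"). Neither section sets an SCL-20 level. Section C says of the screening data that "these data will be anonymized, so that it will not be possible to link the screening data back to the individual patient".

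The baseline interview comes after screening. Section H describes it as "completing a baseline interview at the time of screening or within the week", and section C allows a rescheduled appointment. Section C also places every self-report measure in all three interviews, so the PHQ-9 and SCL-20 are both taken at baseline. Randomization follows that interview, and no second depression threshold is stated.

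For Aim 3, the SAP (Multivariate analyses testing for moderators and mediators) reports that "we included improvement in depression (as well as depression remission in a separate model) in the logistic regression models". It also tests the interaction of each with treatment. It does not say which scale or visit defines remission, or whether women already below the cut-off are left out.

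**The concern.** Aim 3 asks whether reducing depression makes cancer screening more likely. A woman who scores 8 at screening, 4 at the baseline interview and 4 at 12 months has not changed from her study baseline, yet she is classed as remitted. A woman who goes from 3 to 4 has worsened and is also classed as remitted. On the SCL-20 this is possible with no entry floor at all.

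Randomization does not protect this analysis, because remission is observed after randomization and is used as an exposure. The protocol's own premise (section A) is that depressed women are screened less. Women with low baseline scores may therefore be screened more whether or not anything was reduced, and this definition puts them in the remitted group. The SAP's stated adjustment may not catch this. The confounders it singles out are factors unevenly distributed between arms, and baseline depression will tend to be balanced by randomization. The Aim 3 paragraph names no adjustment for it.

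**Working it through.** **No plan figure to reproduce.** The only design calculation in the SAP (356 women per arm, about 80% power, a 10-point difference) concerns cancer screening. No rate or power is given for remission.

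**Step 1. Who already meets the rule at baseline (no assumptions).** PHQ-9 remission is a score below 5, so any baseline-interview score of 0 to 4 qualifies. SCL-20 remission is a score below 0.5, so any baseline below 0.5 qualifies. The screening threshold of 8 does not exclude the first group, because it applies to another administration. Nothing excludes the second.

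**Step 2. How the two definitions relate (no assumptions).** Remission without a fall of more than 50% is possible from PHQ-9 baselines of 5 or 6 (to 3 or 4), 7 (to 4) and 8 (to 4; 4/8 = exactly 50%). From 9 upward it is impossible: 9 to 4 is a fall of 5/9 = 56%. On the SCL-20, 0.50 to 0.45 is remission after a fall of 0.05/0.50 = 10%.

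**Step 3. How often a woman is below 5 at baseline (assumptions only).** The documents give no PHQ-9 mean, SD or retest correlation; their 0.81 is for the SCL-20. Assume a clinic-population PHQ-9 with gamma-shaped margins, rounded and limited to 0–27, and correlation r between the underlying normal scores at screening and baseline. Among women scoring 8 or more at screening, simulation (2 million pairs per setting) gives this share below 5 at baseline:

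| Mean / SD | r = 0.7 | r = 0.81 | r = 0.9 | r = 0.95 |
|---|---|---|---|---|
| 6 / 5 | 13.6% | 7.5% | 2.6% | 0.5% |
| 7 / 6 | 12.6% | 7.2% | 2.6% | 0.6% |
| 8 / 6 | 9.2% | 5.0% | 1.7% | 0.3% |

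Of 800 women, r of 0.7 to 0.9 gives about 14 (0.017 × 800) to 109 (0.136 × 800). At r = 0.95 it is about 2 to 5. A lower mean (5, SD 5) with r = 0.6 raises the share to 25%. The SCL-20 share cannot be estimated this way, because the documents give no level for that scale.

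**Step 4. Whether these women stay below 5.** Add a third score with the same correlation and no true change. At r of 0.7 to 0.9, only about 22 to 36% of the women who were below 5 at baseline are below 5 again. Real recovery would raise this share.

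**Step 5. Effect on a comparison of remission between arms.** If a share q is below the cut-off at baseline and remits equally often in both arms, the risk difference becomes (1 − q) × the difference among women at risk. For an assumed 20% vs 30% among women at risk and q = 5%, it is 0.95 × 10 = 9.5 points. The loss of power is greatest if all of these women stay below the cut-off. The rates are then 0.05 + 0.95 × 0.20 = 24.0% and 0.05 + 0.95 × 0.30 = 33.5%, and power at 356 per arm falls from 0.87 to 0.80. At q = 10% under the same extreme assumption it is 0.73. Step 4 shows that this assumption is too strong.

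**The case against.** The strongest reply is that Aim 3 does not rest on remission. The first exposure named in the SAP is improvement, which the protocol defines against baseline; remission is a second, separate model. This stands, and it limits the point to that model and its interaction. It does not repair the remission variable.

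A reader might also infer that remission dilutes the estimated benefit of CCI. The SAP compares changes in depression between arms and never names remission as an endpoint for that comparison, so this loss is conditional on an analysis that is not specified. If it were done, randomization would be expected to balance women with low baseline scores, giving dilution and not bias. Nor are these women near-certain successes, as Step 4 shows.

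A further tempting reading is that the protocol contradicts itself because remission can occur without meaningful improvement (Step 2). It does not. It defines a change and an end state, and nowhere says that one must contain the other. The case of 8 to 4 also disappears if the rule was meant as at least 50%.

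Finally, the frequency is assumed. In-person recruitment aims to hold the baseline interview on the same occasion, where the correlation may exceed 0.9 and the share may be close to nil. This stands too, and it is a reason to report the count.

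**Conclusion.** The point holds in a limited form. As written, the remission rule can class women as remitted when they had nothing to reduce, and neither document closes the gap. This follows from the text alone. It affects the interpretation of the separate Aim 3 remission model and its treatment interaction. It does not affect the screening comparison or the model based on improvement.

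The size is unknown. About 2 to 14% below PHQ-9 5 at baseline (5 to 8% at r = 0.81) rests on an assumed mean of 6 to 8, SD of 5 to 6 and retest correlation of 0.7 to 0.9. At 0.95 the share is under 1%. The documents do not support treating any of these as the trial's own figure, or concluding that the arm comparison is biased. This is an inexpensive improvement to a secondary model, not a fault that undermines the trial.

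**What to change.** In protocol section F and in the SAP's Aim 3 paragraph:

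- Count remission only among women who did not already meet it at the baseline interview: PHQ-9 of 5 or more for PHQ-9 remission, SCL-20 of 0.5 or more for SCL-20 remission, and both conditions for the either-scale composite.
- Include the baseline-interview depression score in the Aim 3 models.
- Report by arm how many women were below PHQ-9 5 or SCL-20 0.5 at the baseline interview.

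Remission need not also meet the more-than-50% rule; the two definitions can stand side by side.

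The cost is a short addition to each document and a derived flag from data already collected. Eligibility and data collection do not change. The SAP is written in the past tense, so if the models have been run, this is a supplementary run. The remission model loses the women who were not at risk of remitting, and the two scales may have slightly different denominators, which should be shown.
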